7.6 Primary Analysis

The primary analysis will be conducted using a mixed model using all available data. There will be main effects and interactions used to classify the PCWP as of randomized treatment DAPA/control, exercise yes/no, and baseline yes/no. A random subject effect will be utilized to block data on individual participant. The model configured this way provided the means to conduct a likelihood ratio test for the importance of DAPA on altering the PCWP profiles as the test for the primary hypothesis. Statistical contrasts will be utilized to compare PCWP under exercise at the end of the treatment period between groups and the differences in the change in PCWP over the study period between groups. These two hypotheses are a priori specified and will not be adjusted for multiple comparisons as they are intrinsically linked to the primary likelihood ratio test. This statistical model does not per se adjust for measured covariates as fixed effects in the model. The model, however, does include the random effect that effectively "adjusts for baseline" using a random variance term. However, it is acknowledged while the design is randomized, the sample size is relatively small to rely on the large sample balancing properties of randomization to account for all confounding in the study. To this end, we will compute standardized differences for all putative confounding variables captured at baseline prior to randomization. Absolute values for the standardized mean differences (SMD) <10% will be considered support for "balance" between the groups. If there are plausible confounding variables with SMD > 10%, sensitivity analyses will be conducted using standard covariate adjustment methods including propensity score analysis. The propensity score analysis is to help mitigate the number of estimated parameters in the mixed model to help ensure convergence of the estimation process.

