For the more general patient reported outcomes and other clinical assessment that have >2 replications, we will use a more generalized modeling framework that accounts for the actual time from baseline in the repeated measures model. Time varying covariates (e.g., marking the period of bariatric surgery) will also be considered to provide a model framework for the data over time. As with the primary analysis, the treatment group by time interaction terms will serve as the main statistical tests of the treatment effect. As with the primary analysis, additional adjustment for imbalance that was not controlled via randomization will be implemented.

Missing data occur. We will conduct sensitivity analyses using modern machine learning based imputation approaches including chained equations and random forest imputation. Differences in estimates between the imputed and the observed data will be examined through pattern mixture models. Lack of consistency of results may indicate an internal bias, so therefore we will disclose our findings by reporting data analysis under the various data imputation strategies.

Reproducible research principles will be integrated throughout the statistical analysis process. The two primary statistical languages of SAS and R will be utilized. In both cases, version controlled datasets will be utilized for any formal statistical reports. Programming code will be written such that all derivations and assumptions are documented within the source code and accompanying materials (i.e., no human manipulation of raw data values once entered into the master REDCap database). R markdown reports are the preferred study report formats as they allow for each communication of interpretation, raw numeric results and figures/tables.

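### The primary test in section 7.6 is a joint rest/exercise test, but the objective and the 93% power concern exercise PCWP; the exercise contrasts have no written gate, and the end-of-treatment one is not baseline-adjusted

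*Combined protocol and SAP*

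**What the plan says.** Section 7.6 fits a mixed model to PCWP with main effects and interactions of "randomized treatment DAPA/control, exercise yes/no, and baseline yes/no". On dependence between a patient's readings it says only: "A random subject effect will be utilized to block data on individual participant". The primary test is the "likelihood ratio test for the importance of DAPA on altering the PCWP profiles as the test for the primary hypothesis". The reduced model and degrees of freedom are not given. The nearest hint is a later sentence of the same section, about other outcomes: "As with the primary analysis, the treatment group by time interaction terms will serve as the main statistical tests of the treatment effect".

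Two contrasts are declared in advance. One is exercise PCWP at the end of treatment. The other is "the differences in the change in PCWP over the study period between groups", with no stage named. They "will not be adjusted for multiple comparisons as they are intrinsically linked to the primary likelihood ratio test". Nothing says that they are tested only if the likelihood ratio test (LRT) is significant.

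On baseline: "This statistical model does not per se adjust for measured covariates as fixed effects in the model". The section goes on: "The model, however, does include the random effect that effectively" adjusts for baseline, by way of a variance term. Covariate or propensity-score adjustment is offered as a sensitivity analysis where a standardised mean difference (SMD) exceeds 10%.

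The other sections divide as follows:

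- **Exercise only:** section 2 (primary objective) and section 7.5 (93% power by t test, with resting values expected to add to it).
- **Rest and exercise:** the Study Summary (which calls the method a mixed-model analysis of covariance), section 3.4 (rest, feet elevated and 20 W, by MMRM) and section 7.4.

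**The concern.** The test that decides the trial does not ask the question in the primary objective. A joint test can be significant because PCWP fell at rest, and the reader would then turn to the contrasts for the exercise answer. Those are two tests at 0.05 each. Being linked to the LRT is given as the reason for not adjusting them, but a link is not a testing rule.

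The power statement has the same gap: it describes a test that is not the primary one. The feet-elevated reading of section 3.4 also has no level in a yes/no exercise factor.

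Finally, section 7.6 credits the random subject effect with a baseline adjustment. If that is not so for the end-of-treatment contrast, the most direct estimate of the exercise effect carries any chance baseline difference and forgoes precision from data already collected.

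**Working it through.** **Inputs.** From section 7.5: SD 5 mmHg, difference 6 mmHg, 18 per arm, alpha 0.05 (sidedness not stated). From the Study Summary: 41 completers, taken as 20 v 21. Assumed, because the documents give no correlations: a common correlation r of 0.3, 0.5 or 0.7 among a patient's readings. The effects at rest, and the 4 mmHg effects, are also assumptions.

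**1. The plan's own figure.** SE = 5 × √(1/18 + 1/18) = 1.667. Noncentrality = 6/1.667 = 3.6 on 34 df. Two-sided power is 93.8%, which matches the 93%; one-sided would be 97.0%. The figure is correct for an unadjusted two-sample t test on exercise PCWP.

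**2. Power of the test that section 7.6 names.** The model is saturated in treatment × exercise × visit with one random intercept, fitted by ML. LRT = 2 × (full minus reduced log-likelihood), referred to chi-square. Two readings are possible: drop the treatment-by-visit terms (2 df, following the later sentence of 7.6), or drop every treatment term (4 df). Simulated percentage significant:

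| Scenario | r = 0.3 | r = 0.5 | r = 0.7 |
|---|---|---|---|
| 18 v 18, 6 mmHg on exercise only, 2 df | 79 | 91 | 99 |
| Same, 4 df | 91 | 97 | 100 |
| 18 v 18, 6 on exercise and 3 at rest, 2 df | 88 | 96 | 99.8 |
| 20 v 21, 6 mmHg on exercise only, 2 df | 84 | 94 | 99.6 |
| Same, 4 df | 94 | 98 | 100 |
| 20 v 21, 4 mmHg at rest only, 2 df | 49 | 64 | 85 |

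The last row is the chance of a significant primary test with no exercise effect at all. The other rows show that adding resting values can lower power below 93% or raise it, depending on r, the resting effect and the reduced model.

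**3. The two contrasts under the null (20 v 21).** Reading the second as exercise change, its correlation with the end-of-treatment contrast is √((1 − r)/2) = 0.59, 0.50, 0.39. The chance that at least one is positive should therefore lie a little below 1 − 0.95² = 9.75%. Simulation gives 8.8, 9.2 and 9.4%. If change is averaged over stages, it is 9.3, 9.3 and 9.5%. If a gate on the 2-df LRT is implied, the rate is 3.0 to 3.4% when the drug affects neither stage. If PCWP falls 6 mmHg at rest only, the gate is usually open and the two exercise contrasts together are falsely positive in 8.5, 8.9 and 9.5%.

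**4. Baseline and the end-of-treatment contrast.** Treatment is fitted at baseline as well as at 6 months, so each cell has its own mean. With complete data the fitted cell means are the raw cell means, whatever the random-intercept variance. The contrast is then the raw difference at 6 months. Fitting the model to 20 simulated datasets confirmed this, with a largest discrepancy of 7 × 10⁻¹⁴. The change contrast and the 2-df LRT do subtract baseline.

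**5. What that costs.** At 20 v 21 the SE of the baseline difference is 5 × √(1/20 + 1/21) = 1.56 mmHg. A gap of 2 mmHg or more has probability 2 × (1 − Φ(2/1.56)) = 20%, and shifts the expected raw difference by r × 2 = 0.6 to 1.4 mmHg.

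With baseline exercise PCWP as covariate, the residual SD is 5√(1 − r²) = 4.77, 4.33, 3.57. At 18 v 18 and 6 mmHg, noncentrality is 3.77, 4.16, 5.04 and power is 95.6, 98.1 and 99.8%, against 93.8% unadjusted. For 4 mmHg at 20 v 21, the simulated figures are 73, 81 and 93% against 71 to 72%.

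**The case against.** Several points on the other side stand.

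- Section 7.6 does name one primary test, and it agrees with the Study Summary and sections 3.4 and 7.4. Sections 2 and 7.5 are the minority, so aligning section 2 with the profile is a legitimate repair.
- Section 7.5 uses exercise PCWP only as a starting frame and never says that 93% is the LRT's power. At 41 completers the LRT is below 93% only at r = 0.3 under the 2-df reading. If the test-retest figure in 7.5 is an SD of repeat differences, r exceeds 0.5; the section does not say so. A reader might infer that the trial is underpowered. The documents do not support that.
- The primary LRT's own null rate is about 6%. The 9 to 10% applies only if a claim is made on either contrast regardless of the LRT. A fall of 6 mmHg at rest with none on exercise is not anticipated anywhere in the plan.
- A reader might infer that the primary analysis has no baseline adjustment at all. That is wrong for the change contrast and for a treatment-by-visit LRT. There is also a safeguard: a 2 mmHg gap is an SMD of 2/5 = 40%, well above the 10% trigger, if baseline PCWP counts among the variables checked. But this yields a sensitivity analysis and leaves the main end-of-treatment estimate unchanged.

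None of this supplies the missing reduced model, degrees of freedom or gate, or makes the statement about the random effect true for the end-of-treatment contrast.

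**Conclusion.** The point holds, as one to fix before unblinding. The objective and power concern exercise PCWP, while the primary test is a joint test with unstated terms. Its power for 6 mmHg on exercise only runs from 79 to 100% at 18 v 18, and a 4 mmHg fall at rest alone makes the 2-df version significant in 49 to 85% of trials at 20 v 21. The two contrasts carry about 9 to 10% false positives if either can support a claim, and about 3% if a gate is implied and the drug affects neither stage. The end-of-treatment contrast is not adjusted for baseline.

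The percentages rest on SD 5 from section 7.5 and on assumed equal correlations. The mismatch, the missing gate and the raw-difference result do not depend on those values.

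One random intercept also imposes equal variances and correlations, and a reader might take from this a specific inflated error rate. With assumed correlations of 0.7 within session, 0.4 for the same stage across visits and 0.3 otherwise, averaged change is falsely positive in 14.9% and the 2-df LRT in 9.0%. Other assumed sets push the LRT as low as 3.2%. This shows that a single random intercept can mis-state error; it does not estimate by how much, or in which direction, in this trial.

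**What to change.** Reconcile the Study Summary and sections 2, 3.4, 7.4 and 7.5 on the primary question, and name one primary test at two-sided 0.05.

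**If exercise PCWP is primary:** estimate the DAPA minus placebo difference at 6 months (at 20 W, if that is the stage meant in 3.4), adjusted for baseline exercise PCWP. Do this within the MMRM of section 3.4, with unstructured covariance, REML, Kenward-Roger degrees of freedom and a common baseline mean, so that all available data are kept. Give simple ANCOVA as a complete-case check. Drop the separate exercise-change contrast, which becomes the same test once baseline is in the model. Test the profile afterwards, in fixed order.

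**If the profile stays primary:** write out its reduced model and degrees of freedom, restate power for that test, give feet-elevated a level in the model, and test a single baseline-adjusted exercise contrast only if the profile test is significant.

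In either case, remove the statement that the random effect adjusts for baseline, or limit it to the contrasts for which it is true.

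**Cost:** wording only, with no new data. The profile test may become secondary. If PCWP fell equally at rest and on exercise, the LRT would have slightly more power (18 v 18, 6 mmHg at both: 97.8, 99.7 and 100%, against 95.2, 97.7 and 99.8% for simulated ANCOVA). An unstructured matrix over three stages and two visits has 6 × 7/2 = 21 parameters for 41 patients, so a fallback should be named in advance. The exercise readings alone need 3.

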7.7 Moderators of treatment effect

It is plausible that increased obesity may result is differential responses to the DAPA treatment. We will test this using splined fits of BMI. In addition, age group will be examined a priori. The type III estimates of the treatment effect will be compared to the unadjusted analysis to assess the robustness of the randomization process. Graphical displays such as the customary forest plot will be used to present the means and 95% confidence intervals for the estimated responses in these subgroups. Likewise, additional subgroups based on baseline demographic and medical history will be plotted for completeness.

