7.1 Introduction to the Statistical Design

This study will use a 1:1 randomization to active therapy or control. The control group is scientifically necessary because it is expected that there will be longitudinal changes in cardiac function and hemodynamics in the absence of intervention that need to be accounted for in the analysis. The primary endpoint is left ventricular filling pressure, specifically pulmonary capillary wedge pressure (PCWP) measured invasively in the cardiac catheterization lab. Within each endpoint assessment period (described in section 6), a baseline (resting) and exercise assessment of PCWP will be gathered. The analysis plan described below will detail how the longitudinal measurements will be used to objectively test for differences both within group over time and between groups over time.

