7.5 Sample Size Estimation

Based on preliminary data from our previous studies (Borlaug et al 2015, 2016), we know the PCWP is positively correlated within individuals between rest and exercise. Furthermore, the standard deviation of PCWP has been consistently ~5 mmHg, with some proportionality to the mean (i.e., more variability in those with pulmonary hypertension). To initially frame the sample size, we first focus on the exercise PCWP. We expect little, if

Page 19 of 34

any, improvement in PCWP in the control group (some improvement possible due to the Hawthorn effect). We assume the average exercise PCWP in obese HFpEF patients is 30 mmHg and expect a 20% (6 mmHg) reduction in exercise PCWP in patients treated with DAPA compared with patients with placebo. The test-retest variability in exercise PCWP is <5 mmHg.

Based on two sample t test, 36 patients (18 receiving DAPA and 18 placebo) would provide 93% power to detect a difference of 6mmHG or greater in PCWP during exercise workloads between the DAPA and placebo groups, with a common standard deviation of 5 mmHg, at 0.05 significance level. By including resting values of PCWP in the mixed model with repeated measures, this is expected to increase the power further.

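### Section 7.7 uses the gap between type III and unadjusted treatment estimates to check randomisation, which it cannot do, and leaves the source model and term undefined

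*Combined protocol and SAP*

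**What the plan says.** Section 7.7 asks whether the response to the drug varies with obesity and age: "We will test this using splined fits of BMI. In addition, age group will be examined a priori". It then adds: "The type III estimates of the treatment effect will be compared to the unadjusted analysis to assess the robustness of the randomization process". It does not say which model supplies that estimate, whether the model contains a treatment-by-BMI interaction, how BMI is centred, which spline basis or knots are used, or where the age groups are cut.

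The comparator is presumably the primary model of Section 7.6. That is a mixed model with a random subject effect and with treatment, exercise status and baseline status as main effects and interactions. It has no measured covariates. Pre-treatment PCWP is therefore one of the outcome values. The same section says, for the other repeated outcomes and in parallel with the primary analysis, that treatment-by-time interactions carry the test of the drug effect. It also plans covariate-adjusted sensitivity analyses when a standardised baseline difference exceeds 10%, and it names both SAS and R.

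Sections 5.3 and 7.2 describe randomisation as a 1:1 block sequence run by the research pharmacy. No power is claimed for any moderator test.

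**The concern.** Randomisation is a procedure. Its soundness is judged from how the sequence was generated, concealed and followed. A difference between two estimates computed from the resulting data does not bear on that, so the stated purpose of the comparison is invalid whichever model is used.

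The second difficulty is that the number to be compared is undefined. In a section on moderators, an analyst could reasonably take the treatment term from the interaction model. Depending on coding, that term may describe a patient who does not exist, or may mix pre-treatment values into the drug effect. A large gap could then be reported as doubt about the randomisation or the main result when neither is at fault.

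**Working it through.** **1. The plan's own figure.** Section 7.5 gives the inputs: "Based on two sample t test", "36 patients (18 receiving DAPA and 18 placebo) would provide 93% power", "expect a 20% (6 mmHg) reduction in exercise PCWP", "with a common standard deviation of 5 mmHg", "at 0.05 significance level". The noncentrality is 6 / (5 × √(2/18)) = 6 / 1.667 = 3.6. A two-sided noncentral t with 34 df gives 93.8%, in line with the stated 93% (one-sided would give 97.0%). I therefore use 6 mmHg and SD 5 below, with the 41 planned completers from the Study Summary and equal allocation ("This study will use a 1:1 randomization to active therapy or control").

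**2. Assumptions.** The documents give no BMI distribution. I take mean 35 (SD 6), with a range from 33 (SD 5) to 37 (SD 7), and a single continuous outcome with residual SD 5. Simulations used 4,000 to 6,000 trials per setting.

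**3. Uncentred linear interaction.** In Y = a + b·T + c·BMI + d·T·BMI + error, b is the drug effect at BMI 0. Its standard error is approximately (2σ/√n) × √(1 + (mean/SD)²), where 2 × 5/√41 = 1.56 mmHg is the value at mean BMI.

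| Assumed BMI mean (SD) | Inflation | SE of b (mmHg) | Power of b for 6 mmHg |
|---|---|---|---|
| 33 (5) | 6.68 | 10.4 | 8% |
| 35 (6) | 5.92 | 9.2 | 9–10% |
| 37 (7) | 5.38 | 8.4 | 11% |

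In simulation at 35 (6), the SD of b was 10.0.

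True moderation also shifts the location of b. With an effect of −6 at mean BMI and a slope of −0.3 per BMI unit, the effect at BMI 0 is −6 + 35 × 0.3 = +4.5. With a slope of −0.5 it is −6 + 35 × 0.5 = +11.5. The simulated means were +4.5 and +11.2. Every simulated trial was perfectly randomised.

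**4. The same data under other codings** (no moderation, true effect −6):

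| Source of the treatment estimate | Mean | SD |
|---|---|---|
| Unadjusted | −6.0 | 1.53 |
| Additive BMI spline, no interaction | −6.0 | 1.60 |
| Linear interaction, BMI centred | −6.0 | 1.55 |
| Linear interaction, uncentred (effect at BMI 0) | −6.0 | 10.0 |
| Spline interaction anchored at minimum BMI (effect there) | −6.3 | 10.3 |
| Restricted cubic spline interaction, uncentred (effect at BMI 0) | −7.0 | 41.2 |

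**5. The treatment main effect.** Baseline is a level of the outcome in Section 7.6. Before treatment, the expected difference between arms is 0; at follow-up it is −6 for exercise PCWP. A main effect that weights the two occasions equally has expectation (0 + (−6))/2 = −3, half the follow-up effect. Under reference-level coding it is the difference at the reference occasion, which has expectation 0 if that is baseline. Neither is the drug effect, even with no BMI in the model.

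**6. Age in groups.** No cut-points are given, so I used a median split, with the assumed BMI distribution standing in for age. For linear moderation of −0.5 mmHg per unit and n = 41, the continuous interaction test had 41–42% power, against 28–30% for the split and 25% for tertiles. For a step at the centre of the distribution the order reversed: 29% continuous, 36% split.

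**The case against.** The best defence is that Section 7.7 may intend something ordinary: an adjusted estimate set beside the unadjusted one, as Section 7.6 already plans for imbalance. On that reading, the additive row in step 4 applies and the comparison is harmless apart from its label. This stands. A reader might infer that the type III term simply is the effect at BMI zero. The documents do not support that, because they do not say that the estimate comes from an interaction model, nor that BMI is uncentred.

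A reader might also infer that the BMI spline wastes power. That does not hold in general. For linear moderation, a linear test has 41–42% power against 23–30% for splines. For a U-shape the order reverses, with 17% linear against 55–67% for splines. The choice is a trade-off and is not part of this point.

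It is also fair to say that the simulations use one outcome rather than the planned repeated-measures model. They therefore show the direction and scale of the coding problem, not the exact standard error the trial would obtain.

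The defence does not reach two things. The stated purpose is invalid for an additive model as well. And the silence on model and term matters because the resulting number changes greatly with the coding, in a plan that allows two software packages.

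**Conclusion.** The point holds with limits. Without condition: the comparison cannot assess randomisation, and with baseline as an outcome level a treatment main effect is the wrong term. With condition: if the term comes from an uncentred treatment-by-BMI model, its standard error is about 9 to 10 mmHg against about 1.6 (8.4 to 10.4 by formula over the assumed BMI range). It can then differ widely from the unadjusted effect, even in sign, with nothing wrong in the trial. An additive or centred model removes this.

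The loss from grouping age is about 12 percentage points of power if moderation is roughly linear. It rests on an assumed median split and slope, with BMI standing in for age. All moderator tests are weak at this sample size.

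Nothing here suggests that the randomisation is faulty or the primary result unsound, though a reader might infer either. The likelihood ratio test and contrasts of Section 7.6 are defined separately, and the 93% power figure is reproduced.

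**What to change.** - Remove the randomisation check as a purpose in Section 7.7, and describe the comparison as sensitivity to covariate adjustment.
- Name the model and the term. Take the overall effect as the treatment-by-time contrast from a model without moderator interactions, or from one with BMI and age centred at their sample means.
- Test age moderation with continuous age, and keep age groups for display.

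These are wording changes to the SAP; they need no new data and leave the primary analysis alone. The one statistical cost is small: a step-shaped age effect would be tested less efficiently than with a well-placed cut.
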